- Overall response rate, which is defined as the proportion of evaluable subjects who achieve CR or PR, as assessed by the investigators,
- Duration of response will be calculated from the date of initial documentation of a response (CR, or PR) to the date of first documented evidence of progressive disease (or relapse for subjects who experience CR during the study) or death. Subjects who are progression-free and alive or have unknown status will be censored at the last tumor assessment.
- Progression-free survival is defined as the duration from the date of first dose of study drug until the date of first documented evidence of progressive disease (or relapse for subjects who experience CR during the study) or death, whichever comes first. Subjects who are progression-free and alive or have unknown status will be censored at the last tumor assessment.
- Overall survival is measured from the date of first dose of study drug to the date of the subject's death. If the subject is alive or the vital status is unknown, the subject will be censored at the date the subject was last known to be alive.

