12.1. Subject Information

The analysis populations for this study are defined as:

- The Treated Population will consist of all subjects who receive at least 1 dose of study drug (either ibrutinib or nivolumab). The Treated Population will be used for all safety and efficacy analysis unless otherwise stated.
- The Response Evaluable Population will consist of all subjects who receive at least 1 dose of both study drugs (ibrutinib and nivolumab), and have a pretreatment, and at least 1 posttreatment disease assessment; unless no post-baseline scan was performed due to AE possibly related to treatment.
- The Pharmacokinetic/Pharmacodynamic Population will consist of all subjects who receive at least 1 dose of study drug (either ibrutinib or nivolumab) and have at least 1 posttreatment sample collected during treatment to determine the concentration or pharmacodynamic biomarker response.

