12.4. Efficacy Analyses

Part A: Individual best tumor responses and duration of response (defined as the time from first response to progression) will be listed for each dose cohort.

Part B: The following efficacy analyses will be performed to explore the clinical activity of ibrutinib in combination with nivolumab in each cohort in the treated population unless otherwise stated:

- Overall response rate (CR or PR) will be calculated with 95% CI for each disease-specific cohort B1, B2, B3, and B4 on the response-evaluable population.
- Progression-free survival and overall survival at 1 year will be evaluated using Kaplan-Meier method.
- Duration of response and duration of stable disease will be evaluated if there are sufficient data for responders within each cohort.

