1.4. Sample Size Justification

The sample size is calculated based on the following assumptions:

- The overall response rate under null hypothesis is 20%
- The overall response rate under alternative hypothesis is at least 38%
- The probability to mistakenly rejecting the null hypothesis when it is actually true is 0.1 (one-sided).
- The probability to correctly rejecting null hypothesis when alternative hypothesis is true is at least 0.8

Under the above assumptions, the study will enroll approximately 35 subjects to get at least 32 response evaluable subjects in each cohort of Part B (Cohorts B1, B2, B3, and B4).

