2.4. Analysis Sets

2.4.1. Efficacy Analysis Set(s)

The all-treated population is defined as all subjects who have received at least 1 dose of study drugs (either ibrutinib or nivolumab).

The response-evaluable population is defined as all subjects who receive at least 1 dose of both study drugs (ibrutinib and nivolumab), and have a pretreatment, and at least 1 posttreatment disease assessment; unless no post-baseline scan was performed due to AE possibly related to treatment or clinical progression or death.

ORR, DOR, DOSD, PFS and OS will be analyzed using the all-treated population. In addition, ORR will also be analyzed based on response-evaluable, if deemed necessary.

DOR will be analyzed for subjects who achieve a partial response [PR (+L)] or better. DOSD will be analyzed for subjects who achieve a stable disease (SD) or better.

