4. EFFICACY

The primary population for the primary efficacy endpoint, ORR, is the all-treated. Sensitivity analysis will be performed on the response-evaluable population, if deemed necessary. Unless otherwise specified efficacy analyses will be based on the all-treated population.

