4.2. Primary Efficacy Endpoint(s)

4.2.1. Definition

The primary endpoint is ORR, defined as the proportion of subjects who achieve partial response or better [PR(+L) or better], as assessed by the investigators at or prior to initiation of subsequent anti-cancer therapy. The primary efficacy analysis of ORR will be conducted at performed 6 months after the last subject has received the first dose of study medication, or earlier if that subject discontinues study therapy. The analysis will be based on the all-treated population.

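### The Part B primary ORR is on response-evaluable subjects in the protocol but on all-treated subjects in the SAP, which keeps the sample size built on 32 evaluable; one responder count per rule gives opposite results, and the stated power need not carry over

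*SAP*

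**What the plan says.** **Protocol.** Section 12.1 makes the Treated Population the default for efficacy unless stated otherwise. ORR is such an exception. Section 10.1 has it "defined as the proportion of evaluable subjects who achieve CR or PR, as assessed by the investigators", and section 12.4 (like the synopsis) calculates it for cohorts "B1, B2, B3, and B4 on the response-evaluable population".

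**SAP.** Section 4: "The primary population for the primary efficacy endpoint, ORR, is the all-treated". Section 4.2.1 repeats this: "The analysis will be based on the all-treated population". The response-evaluable set becomes a sensitivity analysis. Sections 1.1, 2.4.1 and 4 make that analysis conditional on being judged necessary; section 4.2.2 says without condition that it will be done.

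**Sample size.** SAP 1.4 carries over protocol 12.3 unchanged: ORR 20% against at least 38%, one-sided error 0.1, and "approximately 35 subjects to get at least 32 response evaluable subjects in each cohort of Part B". On power: "The probability to correctly rejecting null hypothesis when alternative hypothesis is true is at least 0.8".

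**Response-evaluable definitions.** Both require a dose of each drug, a pretreatment assessment and at least one later assessment. The exceptions differ. Protocol 12.1: "unless no post-baseline scan was performed due to AE possibly related to treatment". SAP 2.4.1: "unless no post-baseline scan was performed due to AE possibly related to treatment or clinical progression or death".

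**Numerator, CLL only.** SAP 4.2.1 counts partial response with lymphocytosis (PR-L). The protocol's ORR definition names only CR and PR. Its Attachment 6.1 lists PR-L inside the PR row, while footnote 3 there requires the lymphocyte count to be normal or more than halved before a response is called PR.

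**The concern.** Each Part B cohort is asked whether ORR exceeds 20% (protocol 2.2, SAP 1.3) and is to be set against historical results (protocol 2.1). The denominator of that rate should be fixed in advance and be the same in both documents. Here a reader can follow either document. The study is open-label and response is investigator-assessed, so the choice should not stay open once responses are known.

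The direction matters. The protocol's set can drop a subject who progresses or dies before the first scan, which raises the rate. The SAP's primary analysis keeps that subject in the denominator.

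The sensitivity analysis does not close the gap. Suppose three of 35 subjects receive both drugs, have a baseline assessment, and are unscanned because of clinical progression or death. The SAP's response-evaluable set is then 35, identical to all-treated, and the protocol's rate on 32 is reported nowhere.

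The sample size was also not revisited when the SAP changed the population.

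**Working it through.** **Inputs.** Null rate 0.20, alternative 0.38, one-sided alpha 0.1, power at least 0.8, about 35 enrolled and at least 32 evaluable per cohort (protocol 12.3, SAP 1.4). Exact Clopper-Pearson 95% interval (SAP 4.2.2). All tails below are exact binomial.

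**1. The plan's own figure.** Take the smallest r with P(X ≥ r | n, 0.20) ≤ 0.1.
- n=32: r=10, P(X ≥ 10 | 32, 0.20) = 0.090, power P(X ≥ 10 | 32, 0.38) = 0.833.
- n=31: r=10, power 0.799.

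So 32 is the smallest n that reaches 0.8, and the stated figure reproduces for a denominator of 32.

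**2. Same responders, two denominators (35 treated, 32 evaluable).**

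| Responders | Rule | On 32 | On 35 |
|---|---|---|---|
| 12 | Exact 95% CI | 37.5% (21.1 to 56.3), excludes 20% | 34.3% (19.1 to 52.2), includes 20% |
| 10 | One-sided p against 20% | 31.3%, p=0.090 | 28.6%, p=0.146 |

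Neighbouring counts agree. For the interval, 11 responders fail on both (lower limits 18.6% and 16.9%) and 13 pass on both (23.7% and 21.5%). At 0.1, 9 fail on both (p=0.175 and 0.255) and 11 pass on both (0.041 and 0.075). The conflict is therefore one responder count per rule. If evaluable subjects respond at 38%, P(X=12 | 32) = 0.144 and P(X=10 | 32) = 0.110, for each cohort.

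For the interval, two non-evaluable subjects are enough: 12/33 has a lower limit of 20.4%, against 19.1% for 12/35.

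**3. Power on the SAP's primary population.** With n=35 at one-sided 0.1 the cut is 11, since P(X ≥ 11 | 35, 0.20) = 0.075 and P(X ≥ 10 | 35, 0.20) = 0.146.
- If 38% is the all-treated rate: P(X ≥ 11 | 35, 0.38) = 0.835.
- If 38% is the rate among evaluable subjects and k of 35 count as non-responders, power is P(X ≥ 11 | 35 − k, 0.38):

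| k | 0 | 1 | 2 | 3 | 4 | 5 |
|---|---|---|---|---|---|---|
| Power | 83.5% | 80.2% | 76.5% | 72.4% | 67.8% | 62.7% |

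Modelling the dilution as one binomial rate, 0.38 × 32/35 = 0.347, gives P(X ≥ 11 | 35, 0.347) = 0.718. Both methods give about 72% at k=3.

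**4. PR-L.** Protocol 1.2.4 cites ibrutinib results in previously treated CLL/SLL with and without PR-L: 76.2% and 79.2% in one analysis (3 points), 42.6% and 62.6% in another (20 points). These are independent-review rates from other studies, so they show scale only. In B1 the SAP's numerator can raise the rate while its denominator lowers it, and the two may offset.

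**The case against.** The strongest reply has four parts.

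- **The SAP may refine the protocol.** Protocol section 12 leaves specific details to the SAP, Treated is the protocol's default efficacy population, and all-treated is the conservative choice. This supports all-treated as the better primary set. It does not reconcile the documents: the protocol makes an explicit exception for ORR, and the denominator of the primary endpoint is more than a detail.
- **Both rates will be seen.** SAP 4.2.2 commits to the sensitivity analysis and to a listing of responses by visit. That stands in part, but three other SAP sections make the analysis conditional, and its definition is not the protocol's.
- **No binding decision follows.** The hypothesis is worded as evaluating and describing, SAP 4.1.1 tests only where applicable, and no go/no-go rule depends on the interval excluding 20%. This is fair: the opposite results are opposite readings of one cohort, not opposite formal decisions. The sample size does nonetheless state an error rate and a power.
- **The power may be intact.** A reader might infer that the change of population takes power below 0.8. The documents do not support that as a flat statement. With 38% as the all-treated rate, 35 subjects give 83.5%. The fall to about 72% needs 38% to be the evaluable-subject rate and the three remaining subjects to count as non-responders. The first is plausible, because the calculation is tied to evaluable subjects, but it is nowhere stated.

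**Conclusion.** The contradiction is real, applies to all four Part B cohorts, and should be fixed. The two documents name different primary populations for ORR, the SAP retains a sample size based on the population it moved to a sensitivity analysis, and the two response-evaluable definitions differ.

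Its size is bounded. Under the plan's 35/32 allowance, one responder count per rule changes the reading. A reader might take the risk to lie at an observed ORR near 20%. It does not: it arises where the test or lower confidence limit is close to 20%, at observed rates of about 29–31% (one-sided 0.1) or 34–38% (95% interval).

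Power of at least 0.8 need not carry over: 83.5% or about 72%, depending on an assumption that the plan leaves open. The SAP's one-sided 0.025 level, against the design's 0.1, is a separate discrepancy and is not counted in these figures.

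PR-L is a matter of clarification, confined to IWCLL-assessed CLL in B1.

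**What to change.** 1. Name all-treated as the primary ORR population in both documents (protocol synopsis, 10.1 and 12.4), with non-evaluable subjects as non-responders. Put the SAP's response-evaluable definition into protocol 12.1. Make that sensitivity analysis unconditional by deleting the necessity qualifier in SAP 1.1, 2.4.1 and 4.
2. In protocol 12.3 and SAP 1.4, state which population the 38% describes and restate power to match, at one-sided 0.1 with critical value 11/35: 83.5% if all-treated, or about 72% if evaluable with 3 of 35 non-evaluable.
3. State in both documents whether PR-L counts in primary ORR. Report B1 CLL ORR with and without it, and compare each version only with historical rates defined the same way.

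The Amendment 7 rationale says that the primary and secondary objectives have already been analysed and published. Where the primary analysis is complete, the practical form of this fix is to document the change of population and report ORR on both the protocol's and the SAP's sets.

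Cost: wording changes and an extra B1 row in the ORR table. No new data are needed, since SAP 2.7 already ranks PR-L separately from PR. The downside is a lower headline ORR than on evaluable subjects and possibly a lower stated power.

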4.2.2. Analysis Methods

The response rate and its 95% exact (Clopper-Pearson) CI will be calculated. Subgroup analysis will be provided. Sensitivity analysis will be performed using the response-evaluable population.

A listing of tumor response by assessment visit will be provided.

4.3. Exploratory Secondary Endpoints

4.3.1. Duration of Response

Definition

Duration of response is defined as the interval between the date of initial documentation of a response [PR(+L) or better] and the date of first documented evidence of PD (or relapse for subjects who experience CR during the study) or death, whichever occurs first. Subjects who are progression-free and alive, or have unknown status will be censored at the last adequate disease assessment.

Analysis method

Duration of response will be analyzed for subjects with PR(+L) or better. The distribution of duration of response will be estimated using the Kaplan-Meier method. The primary analysis will be based on response data by investigator assessment.

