2.7. Other General Definitions

Year and Month

1 year = 365.25 days and 1 month = 30.4375 days.

Age

Use Age (year) collected in the case report form (CRF), which is the number of integer years from the date of birth to the date of informed consent.

Date of overall response for each time point

Date of assessment at that time point. When different assessments for the time point are performed on different dates, the date of overall response is the date of the last assessment performed when the responses PR(+L) or better [except for biopsies - biopsies of tumor or suspected tumors (such as lymph nodes/nodal masses) or extranodal masses (such as GI biopsy, skin lesions, etc.), cytology assessments], or the date of earliest assessment showing progression when the response is PD or relapse from CR.

Date of response

Date of first observed response [PR(+L) or better]. For CLL patients, time to response is calculated from onset of PRL.

Date of best response

Date of first observed best response [PR(+L) or better]. For instance, for subjects who achieved PR followed by CR, PR will be the initial response and CR will be the best response (the date of evaluation with first time CR is reported is the date of best response). Use the ranking below to choose the best response. The response corresponds to the lowest rank of number is the best response:

Rank	Response
1	CR
2	CRI
3	PR
4	NPR
5	PR WITH LYMPH (PRL)

6	SD or no response
7	PD
8	NE
10	UNK
11	(missing)

Date of progression

Date of first observed progression.

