4.3.2. Duration of Stable Disease or Better

Definition

Duration of stable disease or better is measured from the start of the treatment until the criteria for progression are met.

Analysis method

Duration of SD or better will be analyzed using descriptive summary statistics. Subjects whose progression criteria are not met at clinical cut-off will be censored at the last adequate disease assessment.

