4.3.3. Progression-free Survival and Overall Survival

Definition

PFS is defined as the interval between the date of first dose of study drug and the date of first documented evidence of PD (or relapse for subjects who experience CR during the study) or

death, whichever comes first. Subjects who are progression-free and alive, or have unknown status will be censored at the last adequate disease assessment.

OS is defined as the interval between the date of the first dose of study drug and the date of the subject's death from any cause. If the subject is alive at the time of the cut-off, it will be censored at the last known alive date (the last date among visit date, AE start and end dates, treatment date, disease assessment date, and survival follow up date, and if available, survival sweep date, etc.).

Analysis method

Similar analyses will be applied to OS and PFS as those used for duration of response. The distribution of PFS and OS will be estimated using the Kaplan-Meier method.

The primary analysis of PFS will be based on assessments by investigator. The reason of censoring will be summarized for OS and PFS. The median follow-up duration will be provided. Follow-up duration is defined as OS with reversed censoring, i.e., subject who died will be censored. The Kaplan-Meier method will be used to estimate the median follow-up.

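### SAP 4.3.1 does not require the progression that ends duration of response to follow the response, so a subject who first responds after PD gets a negative duration

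*SAP*

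**What the plan says.** SAP 4.3.1 defines DOR as the interval between "the date of initial documentation of a response [PR(+L) or better] and the date of first documented evidence of PD". Relapse from CR and death are the alternative end events, and the earliest counts. DOR is to be estimated by Kaplan-Meier for subjects with PR(+L) or better. Those who are alive and progression-free, or of unknown status, are censored at their last adequate assessment. Protocol 10.1 words the start and end of DOR in essentially the same way.

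The dates come from SAP 2.7. The date of progression is the "Date of first observed progression". At a visit where the response is PD, the date used is "the date of earliest assessment showing progression when the response is PD or relapse from CR". The date of response is likewise the first one observed. Best response is chosen by rank: "The response corresponds to the lowest rank of number is the best response".

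For ORR, SAP 4.2.1 counts responses "as assessed by the investigators at or prior to initiation of subsequent anti-cancer therapy". PFS has its own definition in SAP 4.3.3: "PFS is defined as the interval between the date of first dose of study drug and the date of first documented evidence of PD", or death.

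Protocol 10.2 states that responses to nivolumab may appear after tumor burden has first increased, and it allowed treatment past progression. Table 22 has a column for SD, PR or CR at the repeat assessment, in which therapy and assessments may go on. Protocol 10.2.1.1 and 10.2.1.2 also describe treatment and scans after progression. Amendment 7 ended treatment after progression.

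**The concern.** Each rule is reasonable alone, but together they leave one sequence without a usable DOR. A subject has PD at one scan, stays on treatment, and shows a first PR or CR at a later scan before any new therapy. That subject is a responder, because only subsequent therapy stops the counting of responses. Being a responder brings the subject into the DOR analysis. The subject's progression date is already fixed at the earlier PD, so DOR would end before it begins.

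The censoring sentence does not help, because it covers subjects who are progression-free or of unknown status. Without a rule, the analyst must decide what to do with the subject once the data are visible.

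**Working it through.** The documents state no DOR figure to reproduce. The Part B sample size rests on ORR and is not touched by this point. The check is date arithmetic on the protocol's own schedule.

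**Inputs**
- Cycle length: 14 days (protocol 3.1).
- Scans: every 5 cycles from Cycle 5 for the first 15 months (protocol Table 1 and Attachment 5).
- Minimum interval from first PD to the repeat assessment: 8 weeks in the text of protocol 10.2, 4 weeks in footnote 1 of Table 22. The two passages need to be reconciled; both are used here only to show the range.
- DOR end rule: the earliest of first PD, relapse and death (SAP 4.3.1), with the progression date from SAP 2.7.

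**Scan days.** Day of Cycle c, Day 1 = 1 + 14 × (c - 1).
- Cycle 5: 1 + 14 × 4 = day 57
- Cycle 10: 1 + 14 × 9 = day 127
- Cycle 15: 1 + 14 × 14 = day 197
- Cycle 20: 1 + 14 × 19 = day 267

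**Literal rule.** DOR = min(first PD, relapse, death) - first response. When first PD precedes first response, the minimum is that PD, and DOR is minus the gap between them:

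| Gap from first PD to first response | DOR |
|---|---|
| 4 weeks (4 × 7) | -28 days |
| 8 weeks (8 × 7) | -56 days |
| Next scheduled scan, Cycle 5 to Cycle 10 (57 - 127) | -70 days |

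**Worked subjects.** The last column counts only end events after the initial response.

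| Sequence | Literal rule | End event after response |
|---|---|---|
| PD day 57, first PR day 127, next PD day 267 | 57 - 127 = -70 | 267 - 127 = 140 |
| PD day 57, first PR day 127, no later PD, death day 300 | 57 - 127 = -70 | 300 - 127 = 173 |
| First PR day 57, PD day 197 | 197 - 57 = 140 | 197 - 57 = 140 |

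The third subject, who follows the usual order, is unchanged. A subject with PR, then PD, then PR again also has a positive DOR under the literal rule. The problem is confined to a first response that follows PD.

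The day numbers are nominal and leave out the 7-day run-in of Cohorts B1 and B2. The sign does not depend on them.

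**The case against.** The strongest reply is that a duration of response presupposes an end after the response, and any sensible analyst would read it so. Protocol 12.4 even describes DOR in that direction, as time from first response to progression. That reading is the right one, and it is why the point is minor. But the protocol 12.4 wording is written for the Part A listings, and it does not alter the single progression date in SAP 2.7. A program that reuses that date, as PFS does, returns a negative value.

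It can also be said that the case is rare. Scans normally run to PD, and under Table 22 a second PD on repeat ends both therapy and assessments. In CLL, isolated treatment-related lymphocytosis is not PD under Attachment 6.1, so it does not create the sequence. All of this stands, and it limits the number affected. Amendment 7 does not remove the case, because its stated rationale is that the primary and secondary objectives had already been analyzed.

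Three stronger inferences should be resisted:
- **That ORR and PFS conflict, or that ORR is inflated.** A subject can be an ORR responder and a PFS event. Both rules are prespecified, and the documents do not say whether the 20% benchmark includes responses after PD. The by-visit listing in SAP 4.2.2 ("A listing of tumor response by assessment visit will be provided") will show such sequences.
- **That the SAP leaves open whether PD must be confirmed.** SAP 2.7 and 4.3.3 use the first PD. Confirmation in the protocol governs continuing treatment and scans.
- **That median DOR would shift by a calculable amount.** That would need a rule such as setting the duration to zero, which neither document contains, or excluding the subject, which SAP 4.3.1 does not allow.

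**Conclusion.** The DOR definition fails as written in a situation the protocol expressly foresees. The error is -28 to -70 days of impossible duration per affected subject, on the nominal intervals above. It arises only if at least one subject has a documented PD, then a first PR(+L) or better, with no subsequent therapy in between. The documents give no expected number, and with none nothing changes.

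DOR is an exploratory secondary endpoint, evaluated only if there are sufficient data for responders (SAP 1.1). ORR, PFS and the sample size are unaffected. Severity is minor: this is a wording correction with one resolution consistent with analyzing DOR for every subject with PR(+L) or better.

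**What to change.** In SAP 4.3.1, define the end of DOR as the first documented PD, relapse or death that occurs after the date of initial response. Read progression-free in the censoring sentence in the same way, as no PD since that response. Add a note that this end date may differ from the SAP 2.7 progression date, which continues to serve PFS.

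The cost is one or two sentences and a separate end-date variable for DOR. No new data, table or analysis is needed. One consequence should be expected: a subject may have a DOR that starts after the PFS event, and the note tells the reader why.
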